10.11.2 Amendment 2 (15 Mar 2021)

Overall Rationale for the Amendment

This protocol has been amended to modify the endpoints related to vital signs, physical examinations, laboratory analyses, and growth assessments to align with the agreed EU Paediatric Investigation Plan. This amendment also includes updates to PDILI discontinuation criteria and participant discontinuation to align with updates throughout the bimekizumab development program. In addition, other minor clarifications have been incorporated.

Section # and Name	Description of Change	Brief Rationale
1.1 Synopsis and 3 Objectives and Endpoints	Modified endpoints for vital signs, physical examinations, laboratory analyses, and growth assessments	To clarify that these safety endpoints cover the whole duration of the study.
1.3 Schedule of Activities, Table 1-1 and Table 1-2 and 10.10 Appendix 10: Abbreviations and Trademarks	Deleted “electronic” from phrase “electronic C-SSRS”	Clarification
1.3 Schedule of Activities, Table 1-1	Footnote m has been revised to clarify timing of Screening visit	Clarification
Section 7.1.1.1 PDILI discontinuation criteria	Changed “immediate and permanent discontinuation” to “immediate discontinuation”	Changed as IMP is not always permanently withdrawn in cases where there is alternative explanation for raised LFTs.
Section 7.2 Participant discontinuation/withdrawal from the study	For clarification, added specific infection-related withdrawal criterion	To ensure that participants with serious or recurrent infections not responding to standard therapies are not exposed to immunomodulatory therapies until their infection is resolved. This is in line with

		most biologic therapies, including other anti-IL17s.
Section 10.4 Appendix 4: Contraceptive Guidance and Collection of Pregnancy Information	Footnote c has been deleted from the Highly Effective Contraceptive Methods table.	Correction; not applicable to bimekizumab.

PUBLIC COPY

This document cannot be used to support any marketing authorization application and any extensions or variations thereof

Table 6–2:	Definitions of Markedly Abnormal Haematology Values.....	63
Table 6–3:	Definitions of Markedly Abnormal Biochemistry Values.....	63
Table 6–4:	Definitions of Markedly Abnormal Liver Function Tests.....	64
Table 6–5:	Definitions of Markedly Abnormal Vital Signs.....	64
Table 6–6:	Growth Chart for BMI1 (kg/m ²) by Age and Sex.....	66
Table 6–7:	Growth Chart for Height1 (cm) by Age and Sex.....	67
Table 6–8:	Growth Chart for Weight1 (kg) by Age and Sex.....	67
Table 6–9:	Blood Pressure 99 th Percentile Values1 (mmHg) by Age, Sex and Height Percentile.....	68
Table 6–10:	Growth Chart for Weight1 (kg) by Age and Sex.....	108
Table 6–11:	Growth Chart for Weight1 (kg) by Age and Sex.....	109

LIST OF FIGURES

Figure 1–1:	Study Schematic.....	14
-------------	----------------------	----

VERSION HISTORY

This Statistical Analysis Plan (SAP) for study PS0020 is based on the protocol amendment 3 dated 08 Mar 2022.

SAP Version	Approval Date	Change	Rationale
1.0	18 Feb 2021	Not applicable	Original version
2.0	22 Oct 2021	Amendment	Protocol Amendment 2 and clarifying language throughout document.
3.0	09 Apr 2025	Amendment	Protocol Amendment 3 and Database Lock

Details about the changes in this SAP amendment can be found in Section [6.4.1](#).

LIST OF ABBREVIATIONS

List of Abbreviations

ADAb	antidrug antibody
ADaM	Analysis Data Model
AE	adverse event
ALP	alkaline phosphatase
ALT	alanine aminotransferase
AST	aspartate aminotransferase
ATC	Anatomical Therapeutic Chemical
BKZ	bimekizumab
BMI	body mass index
BSA	body surface area
CDLQI	Children's Dermatology Life Quality Index
CI	confidence interval
CSR	clinical study report
C-SSRS	Columbia Suicide Severity Rating Scale
CTCAE	Common Terminology Criteria for Adverse Events
CV	coefficient of variation
DMC	Data Monitoring Committee
EDV	early discontinuation visit
EMA	European Medicines Agency
E-R	exposure-response
ES	Enrolled Set
HLT	high level term
IBD	inflammatory bowel disease
ICH	International Council for Harmonisation
IGA	Investigator's Global Assessment
IMP	investigational medicinal product
LLN	lower limit of normal
LLOQ	lower limit of quantification
LOCF	last observation carried forward
MedDRA	Medical Dictionary for Regulatory Activities

List of Abbreviations

NAb	neutralizing antibodies
OC	observed case
OLE	open label extension
OLS	Open Label Set
PASI	Psoriasis Area and Severity Index
PBO	placebo
PD	pharmacodynamic
PDILI	potential drug-induced liver injury
PHQ-9	Patient Health Questionnaire-9
PK	pharmacokinetic
PK-PPS	Pharmacokinetic Per Protocol Set
PSO	psoriasis
PT	preferred term
Q4W	every 4 weeks
QOL	Quality of Life
RS	Randomized Set
SAP	statistical analysis plan
sc	subcutaneous(ly)
SFU	Safety Follow-up
SIB	suicidal ideation and behavior
SDG	Standardised Drug Grouping
SMQ	Standardized MedDRA Query
SOC	system organ class
SS	Safety Set
TB	tuberculosis
TEAE	treatment-emergent adverse event
TEMA	treatment-emergent markedly abnormal
ULN	upper limit of normal
WHO	World Health Organization
WHO-DD	WHO Drug Dictionary

PUBLIC COPY

This document cannot be used to support any marketing authorization application
and any extensions or variations thereof

1 INTRODUCTION

PS0020 is an open-label, randomized study assessing the pharmacokinetics (PK), safety, and efficacy of 2 doses of bimekizumab in adolescents with moderate to severe plaque psoriasis (PSO). This Statistical Analysis Plan (SAP) prespecifies the analyses for endpoints in PS0020, including PK, safety, efficacy, quality of life (QOL), and immunogenicity. Results obtained from the analyses in this SAP will serve as the basis of the clinical study report (CSR) for PS0020.

1.1 Objectives and Endpoints

Table 1–1: Objectives and Endpoints

Objectives	Endpoints
Primary	

 To assess the PK of bimekizumab administered subcutaneously (sc) in adolescents with moderate to severe plaque PSO 	
 Bimekizumab plasma concentrations
Secondary	

 To evaluate the safety of bimekizumab in adolescents with moderate to severe plaque PSO 	
 Treatment Emergent Adverse Events (TEAEs) 
 Serious TEAEs TEAEs leading to discontinuation of investigational medicinal product (IMP) TEAEs leading to withdrawal from the study Selected safety topics of interest (including infection [serious, opportunistic, fungal, and tuberculosis (TB)], inflammatory bowel disease [IBD], and injection site reactions) with onset occurring from day of first dose through 20 weeks after final dose of investigational medicinal product (IMP) adjusted by duration of participant exposure to IMP Change from Baseline in vital signs and physical examination findings Change from Baseline in laboratory analyses (chemistry and hematology) Growth assessment, as assessed by the change in height and weight

Objectives	Endpoints

 To evaluate the efficacy of bimekizumab in adolescents with moderate to severe plaque PSO 	
 Psoriasis Area and Severity Index (PASI) 90 (PASI90) response at Week 16 Investigator's Global Assessment (IGA) 0/1 response (Clear [0] / Almost Clear [1] with at least 2-category improvement from Baseline) at Week 16 PASI75 response at Week 4

 To evaluate the immunogenicity of bimekizumab in adolescents with moderate to severe plaque PSO 	
 Anti-bimekizumab antibody detection prior to and following IMP administration

 To evaluate the change in quality of life in adolescents with moderate to severe plaque PSO 	
 Change from Baseline in Children's Dermatology Life Quality Index (CDLQI) response (total score) at Week 16
Other	

 To assess the efficacy of bimekizumab over time in adolescents with moderate to severe plaque PSO 	
 PASI50 response over time PASI75 response over time PASI90 response over time PASI100 response over time Absolute and percent change from Baseline in PASI score over time IGA 0/1 response (with at least 2-category improvement from Baseline) over time IGA 0 response (with at least 2-category improvement from Baseline) over time Scalp-specific IGA (scalp IGA) response (Clear or Almost Clear with at least 2-category improvement from Baseline for participants with scalp PSO at Baseline) over time

 To assess the exposure (PK)-response relationship with selected clinical outcomes in adolescents with moderate to severe plaque PSO 	
 The relationship between plasma bimekizumab exposure and, though not limited to, the following clinical outcomes: PASI score over time, PASI change from Baseline, IGA score over time, IGA change from Baseline

Objectives	Endpoints

 To assess the change in quality of life over time in adolescents with moderate to severe plaque PSO 	
 Change from Baseline in CDLQI response over time CDLQI 0/1 response over time

1.2 Study Design

In this Phase 2, multicenter, randomized, open-label study, the PK, safety, and efficacy of bimekizumab in male and female adolescents (from 12 to <18 years of age) with moderate to severe plaque PSO will be assessed.

The PK, safety, and efficacy of bimekizumab will be evaluated by treating at least 20 participants in each of 2 dose groups (for a total of at least 40 participants evaluable for PK). Both doses are expected to be efficacious based on exposure-response (E-R) predictions. Dose A (320mg every 4 weeks [Q4W] in participants ≥ 65 kg and 160mg Q4W in participants <65kg) is predicted to provide the same systemic bimekizumab exposure as the 320mg Q4W adult dose, and Dose B (64mg Q4W in participants ≥ 65 kg and 32mg Q4W in participants <65kg) is aimed at providing a lower systemic bimekizumab exposure. Weight-based dosing during the Initial Treatment Period will be based on the participant's weight at Baseline.

This study will consist of the following periods:

- Screening Period: up to 5 weeks
- Initial Treatment Period: 20 weeks (5 doses of bimekizumab; administered at Baseline, Week 4, 8, 12, and 16 followed by 4 weeks of observation)
- Open-label Extension (OLE) Period: 104 weeks (bimekizumab administration starts at Week 20 if participant is eligible)
- Safety Follow-up (SFU) Period: 20 weeks after the final dose of bimekizumab

After the Screening Period of up to 5 weeks, eligible participants will be randomized to 1 of the 2 dose groups. The randomization will be stratified by weight category. During the Initial Treatment Period, participants will receive 5 doses of open-label bimekizumab (at Weeks 0 [Baseline], 4, 8, 12, and 16). Participants who complete the Initial Treatment Period, tolerate the treatment, and achieve an IGA response ≤ 2 at Week 20 may continue bimekizumab treatment at the same dose level in the OLE Period.

All available study PK data and clinical data (including selected efficacy and safety data) starting from when 25% of participants have reached Week 16 will be assessed periodically until all participants have completed the Initial Treatment Period. The Phase 3 study (PS0021) dosing will be determined from this information. Upon identification of the PS0021 dose, study participants in PS0020 may switch to the PS0021 dose at the Investigator's discretion during the 104-week OLE Period. Participants who do not tolerate the IMP or who have an IGA response ≥ 3 (on a scale from 0 to 4) at Week 20 will be withdrawn from the study. Each participant will complete the SFU Period of 20 weeks following his/her final dose of bimekizumab.

During the Initial Treatment Period, IMP will be administered by a health care professional at the study site. In the OLE Period, Dose A and Dose B may be administered at the study site or at

home, as indicated in the Schedule of Activities in the protocol. Home visits are encouraged during the OLE Period upon agreement of the Investigator, study participant, and his/her caregiver. Dose A of the IMP may be administered by a health care professional, caregiver, or the study participant (once he/she becomes 18 years of age). Administration of Dose A by the caregiver or study participant is optional and requires training. Dose B will be administered by a health care professional, whether at home or at the study site, to ensure accurate dosing of the lower volume of IMP.

[figure not shown]
The end of the study is defined as the date of the last participant's last visit. The study design of PS0020 provides participants who are receiving benefit from bimekizumab therapy with the opportunity to receive active treatment for a total of 120 weeks.

Safety assessments will be made by ongoing monitoring and evaluation of adverse events (AEs) and other safety topics of interest specific to bimekizumab. Safety topics of interest for this study include infections (serious, opportunistic, fungal, and TB), IBD, injection site reactions, and neuropsychiatric AEs (including suicidal ideation/behavior [SIB]-related AEs). Additionally, in keeping with the adult bimekizumab program, the following topics will also be closely monitored: neutropenia, hypersensitivity (including anaphylaxis), major cardiovascular events, liver function test changes/enzyme elevations, and malignancies. Additional safety assessments will include physical examinations (including growth assessments) and pregnancy testing for female participants of childbearing potential.

An independent external Data Monitoring Committee (DMC) will periodically review and monitor safety data from this study. An IBD Adjudication Committee and a Neuropsychiatric Adjudication Committee will also periodically review data from this study. Details will be provided in separate IBD and Neuropsychiatric Adjudication Committee charters.

A schematic of the design of PS0020 is provided in [Figure 1-1](#).

Figure 1–1: Study Schematic

IGA=Investigator's Global Assessment; IMP=investigational medicinal product; OLE=Open-label Extension; PK=pharmacokinetics; Q4W=every 4 weeks
 Note: All available study PK data and clinical data (including selected efficacy and safety data) starting from when 25% of participants have reached Week 16 will be assessed periodically until all participants have completed the Initial Treatment Period. The Phase 3 study (PS0021) dosing will be determined from this information. Upon identification of the PS0021 dose, study participants in PS0020 may switch to the PS0021 dose at the Investigator's discretion during the 104-week OLE Period.

Note: Participants who do not tolerate the IMP or who have an IGA response ≥ 3 (on a scale from 0 to 4) at Week 20 will be withdrawn from the study.

^a Dose A is predicted to provide the same systemic bimekizumab exposure as the 320mg Q4W adult dose.

^b Dose B is aimed at providing a lower systemic bimekizumab exposure than Dose A.

2 STATISTICAL HYPOTHESES

The primary variable of this study is bimekizumab plasma concentrations. The PK data will be subject to a population PK analysis which will be described in a separate analysis plan.

No formal hypothesis testing or statistical inference will be conducted for the secondary efficacy variables, including safety, efficacy, immunogenicity, and QOL variables. All analyses will be descriptive.

3 SAMPLE SIZE DETERMINATION

The number of study participants, at least 40 total participants randomized 1:1 across the 2 dose arms, is considered to be sufficient to assess bimekizumab population PK and E-R in adolescents. The sample size is based on simulations from an adult PASI E-R model, adjusted for body weight differences in PK for adolescents (ie, allometric scaling in clearance and distribution volume) and assuming the same efficacy response in adolescents as in adults (ie, same parameter estimates for simulation were assumed). A total of 40 participants allocated evenly to 2 dose arms was found in the modeling and simulation to be sufficient for the estimation of PK and pharmacodynamics (PD) parameters with precision in a combined adult-adolescent analysis. Approximately 58 participants will be screened to achieve the sample size of at least 40 participants.

4 POPULATIONS FOR ANALYSIS

4.1 Analysis Sets

4.1.1 Enrolled Set

The Enrolled Set (ES) will consist of all participants who have given informed consent/assent.

4.1.2 Randomized Set

The Randomized Set (RS) will consist of all randomized participants. Unless otherwise stated, efficacy analyses will be based on the RS and as randomized for the Initial Treatment Period.

4.1.3 Safety Set

The Safety Set (SS) will consist of all participants that receive at least 1 dose of the IMP. Safety analyses will be based on the SS and as treated.

4.1.4 Pharmacokinetics Per-Protocol Set

The Pharmacokinetics Per-Protocol Set (PK-PPS) will consist of all randomized participants who receive at least 1 dose of the IMP and provide at least 1 quantifiable plasma concentration post-dose without important protocol deviations that would affect the concentration. Pharmacokinetic variables will be analyzed for all participants in the PK-PPS and will be summarized as randomized.

4.1.5 Open-label Set

The Open-label Set (OLS) will consist of all study participants who receive at least 1 dose of study medication at or after Week 20 in the OLE Period (including the Week 20 dose). The OLS will be the basis for analysis of data from OLE Period. OLS analyses will be based on the SS and as treated.

For summaries using both PK-PPS and OLS, participants will be summarized as randomized.

Immunogenicity analyses will be based on SS or OLS, and participants will be summarized as randomized.

5 STATISTICAL ANALYSES

5.1 General Considerations

All available study PK data and clinical data (including selected efficacy and safety data) will be analyzed when all participants have completed the Initial Treatment Period and at the end of the study. The analysis performed when all participants have completed the Initial Treatment Period will be used for determination of PS0021 dose selection and will not be considered as an interim analysis or provided in an interim CSR.

For by-visit tables summarizing efficacy data, the SFU visit should not be included, but SFU efficacy data should be listed. By-visit tables summarizing safety data should include the SFU visit for the ITP + OLE and OLE summaries. However, SFU should not be included in by-visit safety tables for the ITP alone, due to low sample size.

Descriptive statistics will be displayed to provide an overview of the study results. Summary statistics will consist of frequency tables for categorical variables. The number and percentage of study participants in each category will be presented. The denominator for percentages will be

based on the number of participants appropriate for the purpose of analysis. For continuous variables, summary statistics will consist of the number of available observations, arithmetic mean, standard deviation (SD), median, minimum, and maximum, unless stated otherwise.

Study participants with missing data will be accounted for using the following approaches:

- All efficacy data collected later than 33 days—derived as 28 days allotted for the planned dosing interval plus 5 days allotted for the maximum allowable visit window during either study period—and all safety data that are collected later than 140 days after the last administration of study treatment will be treated as missing and subject to imputation as applicable.
- For summaries of demographics and Baseline characteristics: percentages will be based on all study participants in the relevant analysis set and a “Missing” category (corresponding to study participants with missing data for the variable being summarized) will be included as the last row in the list of categories being summarized, if at least one dose group has a value missing.
- All summaries of PK concentrations will be based on the observed values. No imputation of missing data will be used.
- For efficacy and safety variables, summaries will be typically based on the observed data for the variable being summarized. As the denominator may be different from the number of study participants in the analysis set being considered, the denominator will be displayed in the table. The general format for displaying this will be “n/Nsub (%)”. Selected efficacy variables will be imputed for their missing data as outlined in Section 5.1.1.7.3. Partial dates for AEs will be imputed as outlined in Section 5.1.1.7.5.
- For secondary efficacy variables of responses, 95% Clopper-Pearson confidence intervals (CIs) will be provided for responder rates (PASI90 at Week 16, PASI75 at Week 4, and IGA0/1 at Week 16) in each dose group. For Change from Baseline in CDLQI response at Week 16, 95% CIs will be provided for the mean change for each dose group.

Percentages will be presented to 1 decimal place. If the percentage is 100%, a decimal will not be presented. If the count is 0, the percentage will not be presented. For percentages representing proportions, for the purpose of the tabulations the lower and upper confidence limits for the percentages will be truncated at 0 and 100% respectively.

In order to avoid issues caused by inaccurate floating-point representation of numeric values, the ADaM (Analysis Data Model) variables AVAL (analysis value), CHG (change) or PCHG (percentage change) will be rounded to twelve decimal places prior to the comparison to the threshold. This should be applied exclusively during the derivation of new response parameters (subsequently retained in the dataset) or critical value variables and does not imply inherent rounding on AVAL, CHG or PCHG variables which are retained unrounded in the final ADaM dataset.

If the calculated lower bound for a confidence interval of a proportion is less than 0, the lower bound should be presented as 0. Similarly, if the upper bound of the confidence interval exceeds 100, the upper bound should be presented as 100. Decimal places for descriptive statistics will be subject to the following rounding rules:

- “n” will be an integer.
- Mean, SD, and median will use 1 additional decimal place compared to the original data.
- Coefficient of variation (CV) [%] will be presented with 1 decimal place.
- Minimum and maximum will have the same number of decimal places as the original value.

Per protocol, visit windows are ± 3 days from the date of first dose for the Initial Treatment Period and ± 5 days for the OLE Period. For by-visit presentations, data from unscheduled visits should generally not be included, since sample sizes for unscheduled visits are expected to be small and are often not representative of the whole sample. One exception is Baseline, where data from unscheduled visits are considered if this is the only value prior to the first administration of study medication. Another exception where data from unscheduled visits should be considered is any by-visit table which includes post-Baseline rows for minimum, maximum and/or last measurements. In case of repeated laboratory tests at a particular visit, the last measurement should generally be used for visit presentation in by-visit summaries.

A complete set of data listings containing all documented data and all calculated data (eg, change from Baseline) will be generated.

All analyses will be performed using SAS® version 9.4 or later (SAS Institute, Cary, NC, US). All tables and listings will use Courier New font size 9.

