BSA	X		X			X			X			X			X			X			X			X				X	X
PASI	X		X			X			X			X			X			X			X			X				X	X
IGA	X		X			X			X			X			X			X			X			X				X	X
CDLQI	X		X						X						X						X							X	
Scalp IGA ⁱ	X		X						X						X						X							X	
C-SSRS ^m	X	X	X	X	X	X	X	X	X	X	X	X	X	X	X	X	X	X	X	X	X	X	X	X	X	X	X	X	X
PHQ-9	X		X			X			X			X			X			X			X			X				X	
Adverse events	X	X	X	X	X	X	X	X	X	X	X	X	X	X	X	X	X	X	X	X	X	X	X	X	X	X	X	X	X

Table 1-2: Schedule of study assessments – Open-label Extension Period

Protocol activity	Week ^a	OLE Period																											
Concomitant medication		X	X	X	X	X	X	X	X	X	X	X	X	X	X	X	X	X	X	X	X	X	X	X	X	X	X	X	X
IVRS/IWRS		X		X			X			X			X			X			X			X			X			X	X
IMP administration ^j		X ^k	X	X	X	X	X	X	X	X	X	X	X	X	X	X	X	X	X	X	X	X	X	X	X	X	X	X	

AE=adverse event; BKZ=bimekizumab; BSA=body surface area; CDLQI=Children's Dermatology Life Quality Index; C-SSRS= Columbia Suicide Severity Rating Scale; EDV=Early Discontinuation Visit; IGA=Investigator's Global Assessment; IGRA=interferon-gamma release assay; IMP=investigational medicinal product; IVRS=interactive voice response system; IWRS=interactive web response system; OLE=Open-label Extension; PASI=Psoriasis Area and Severity Index; PHQ-9=Patient Health Questionnaire 9; PK=pharmacokinetics; scalp IGA=scalp-specific Investigator's Global Assessment; SFU=safety follow up; W=week

Note: All available study PK data and clinical data (including selected efficacy and safety data) starting from when 25% of participants have reached Week 16 will be assessed periodically until all participants have completed the Initial Treatment Period. The Phase 3 study (PS0021) dosing will be determined from this information. Upon identification of the PS0021 dose, study participants in PS0020 may switch to the PS0021 dose at the Investigator's discretion during the 104-week OLE Period.

Note: A participant's weight-categorized dose may only be changed during the OLE Period after assessment of weight change by the Investigator at a scheduled clinic visit and if the participant's weight crosses the 65kg boundary at 2 consecutive weight assessments. If a participant's body weight decreases from the ≥65kg to <65kg group during the OLE Period, the participant should be discussed with the Medical Monitor to determine whether a dose adjustment is needed.

^a Visit windows of ±5 days.

^b Safety Follow-up Visit should occur 20 weeks after the final dose of IMP.

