5.6 Safety Analysis

Safety variables will be analyzed for all study participants in the SS (for the Initial Treatment Period and combined Initial Treatment Period and OLE Period when needed), and in the OLS (for the OLE Period). In general, safety data that are collected within 140 days of the last study drug dose (covering the 20-week SFU Period) will be attributed to the period in which the participant was before initiating the SFU Period and will be analyzed according to the most recent dose prior to or at the time of the collection.

By-visit tables summarizing safety data should include the SFU visit for the ITP + OLE and OLE summaries. However, SFU should not be included in by-visit safety tables for the ITP alone, since only a few participants will not enter the OLE.

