Out of window exclusion rules for bimekizumab plasma concentration summaries and figures:

- A sample will be considered out of window relative to the current dose and will be excluded from the summaries and graphs if the sample is collected >1 day after the dose administered at this visit. This excludes samples collected at an EDV visit, including Week 20 (if the participant did not enter the OLE Period) or Week 124 and Week 1, where a dose will not be administered at that visit.
- Alternatively, a sample will be considered out of window relative to the previous dose and will be excluded from the summaries and graphs if the sample is collected <14 days or >42 days after the previous dose, and the sample was collected prior to the dose at that visit (should a dose be scheduled). Week 1 will be excluded from this rule.

The PK data will be subject to a population PK analysis and will be described in a separate analysis plan and reported independently.

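### SAP day limits leave every safety follow-up sample out of the PK summaries and drop late in-window follow-up values from the by-visit safety tables; the 33-day efficacy limit is a lesser ambiguity

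*SAP*

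**What the plan says.** **PK.** SAP 5.7.1.1 names SFU among the visits at which plasma bimekizumab, the primary variable, is assessed, and plans descriptive statistics and plots for each scheduled visit. SAP 5.9 plans a final PK and antibody analysis that includes SFU. The out-of-window rules in 5.7.1.1 then drop a sample from summaries and graphs when "the sample is collected <14 days or >42 days after the previous dose". Week 1 is the only exemption from that rule.

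**Safety.** SAP 5.1 states that "all safety data that are collected later than 140 days after the last administration of study treatment will be treated as missing". SAP 5.6 states that "By-visit tables summarizing safety data should include the SFU visit for the ITP + OLE and OLE summaries"; SAP 5.1 says the same. The protocol (Table 1-2 footnotes) says that the "Safety Follow-up Visit should occur 20 weeks after the final dose of IMP" and gives "Visit windows of ±5 days". Table 1-1, which also has an SFU column, gives ±3 days.

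**Efficacy.** SAP 5.1 treats efficacy data collected more than 33 days after the last administration as missing. The 33 is "derived as 28 days allotted for the planned dosing interval plus 5 days allotted for the maximum allowable visit window during either study period". The same section says "Per protocol, visit windows are ± 3 days from the date of first dose for the Initial Treatment Period", and then gives ±5 days for the open-label extension (OLE) without repeating the anchor.

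**The concern.** Each limit counts days from the last dose, and each meets a scheduled visit at or beyond that limit. A programmer who follows the PK rule produces an empty SFU row in the summary of the primary variable, although the plan calls for that row. A programmer who follows the safety rule keeps SFU laboratory values, vital signs, height and weight from early and on-time visits and blanks them for visits a day or more late but still allowed. The 33-day limit is evidently meant to keep in-window visits, but it has room for one deviation where two may occur: the last dose can be early and the next visit late.

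**Working it through.** **Inputs.** Dosing interval 28 days. Windows ±3 days (protocol Table 1-1) and ±5 days (Table 1-2). SFU 20 weeks after the final dose. PK limits 14 and 42 days, safety limit 140 days, efficacy limit 33 days (SAP 5.7.1.1 and 5.1). No dose is given at Week 124 (SAP 5.7.1.1), and none at Week 20 for participants who do not enter the OLE (Table 1-2 footnote).

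**The plan's own figures.** 28 + 5 = 33 days. 20 × 7 = 140 days. The protocol's maximum duration of 145 weeks equals 5 + 120 + 20, which places the last dose at Week 120; a Week 124 dose would give 5 + 124 + 20 = 149.

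**1. PK.** The earliest in-window SFU sample is at 140 − 5 = 135 days, which is 135 − 42 = 93 days past the limit. No dose is scheduled at SFU, so the rule's condition about sampling before that visit's dose does not take SFU out of it. All SFU samples are excluded, with no assumption about visit timing. By contrast, SAP 5.7.1.4.1.6 assigns antibody samples to a visit within ±21 days and names SFU. PK and antibody samples share one schedule (SAP 5.7.1.4), so the same draw would appear in the antibody by-visit table and be absent from the PK table.

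**2. Safety.**

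| Window | SFU days allowed | Days set to missing | Share of allowable days |
|---|---|---|---|
| ±5 | 135–145 | 141–145 | 5/11 = 45% |
| ±3 | 137–143 | 141–143 | 3/7 = 43% |

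These are shares of visits only if visits spread evenly over the window, which is an assumption. With normally distributed deviations centred on the target (SD 1.5 to 3 days, rounded to whole days and cut at the window), about 37% to 43% of visits fall after day 140.

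**3. Efficacy.** If windows run from first dose, gap = 28 + (visit deviation) − (dose deviation).

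- Week 120 dose to Week 124 visit, ±5 each: 18 to 38 days. Gaps of 34, 35, 36, 37 and 38 days arise from 5, 4, 3, 2 and 1 of the 11 × 11 = 121 deviation pairs. That is 15/121 = 12% if deviations are uniform and independent, or about 2% to 6% with bell-shaped deviations of SD 2 to 3 days.
- Week 16 dose to Week 20 visit, ±3 each, only for participants without a Week 20 dose: 22 to 34 days, with 1/49 = 2% of pairs above 33.
- If windows run from the previous dose instead, the maxima are 28 + 5 = 33 and 28 + 3 = 31 days, and nothing is lost.

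A Week 124 value set to missing becomes nonresponse for the PASI and IGA response rates (SAP 5.1.1.7.3, 5.5.1, 5.5.3). Absolute PASI thresholds, PASI change and CDLQI 0/1 are observed-case summaries, so there the participant leaves the denominator.

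**The case against.** Several stronger readings are tempting, and the documents do not support them.

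- *All in-window SFU, Week 124 and Week 20 visits are lost.* For safety and efficacy, only the late ones are. The loss is complete only for SFU PK samples.
- *The data are thrown away.* SAP 5.1 plans listings of all documented data, and 5.7.1.1 lists all PK concentrations. Population PK has its own plan, and PS0021 dose selection rests on data through the Initial Treatment Period.
- *Efficacy conclusions are at risk.* The secondary endpoints are at Weeks 4 and 16. Participants who stop treatment earlier are already nonresponders for the binary endpoints under the composite strategy. Week 20 matters only for the few who do not enter the OLE.
- *The 140-day limit is wrong in itself.* The protocol defines both TEAEs and TEMA laboratory values through the final dose plus 20 weeks (9.4.1.1, 9.4.1.3), so for those the SAP is right.

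It can also be argued that the PK exclusions are aimed at departures from the scheduled dose and sampling window, which a scheduled SFU sample is not. That is probably the intent, but the rule as written catches SFU. Next, SAP 5.1 assigns windows to the two treatment periods and not to SFU by name. That does not help: with no window at all, any SFU visit after its target day would still be blanked. Last, the efficacy point depends on an anchor that the SAP states outright only for the Initial Treatment Period, and the 28 + 5 derivation fits a previous-dose anchor. That stands, and it is why the efficacy point is minor.

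**Conclusion.** Wrong as written on two counts, and ambiguous on a third.

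1. The 42-day rule empties the SFU row of the PK summaries and figures. The size is 100% of SFU samples, and no assumption is needed.
2. The 140-day rule conflicts with the instruction to show SFU in the ITP + OLE and OLE by-visit safety tables. It removes 5 of 11 or 3 of 7 allowable days. A percentage of visits needs an assumed distribution of visit timing: about 37% to 45% over the cases tried.
3. The 33-day limit can turn an in-window Week 124 visit into a nonresponse, but only if OLE windows run from first dose. The share is then about 2% to 12%, depending on the assumed spread of visit deviations. The Week 20 effect is negligible.

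All these analyses are descriptive. The harm is incomplete or misleading tables; no test, adverse event definition or secondary endpoint changes.

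**What to change.** - **PK (SAP 5.7.1.1):** exempt SFU from the 14-to-42-day rule and give it a window around day 140. The ±21 days already used for antibody samples from the same draw is a natural choice.
- **Safety (SAP 5.1):** for by-visit safety summaries, accept SFU data up to 140 days plus the visit window (145 days). State explicitly that TEAE and TEMA definitions keep the 140-day limit; otherwise laboratory values from days 141 to 145 would enter TEMA tables against the protocol. Name the window that applies to SFU.
- **Efficacy (SAP 5.1):** either use 38 days in the OLE (28 + 5 + 5) and 34 days in the Initial Treatment Period (28 + 3 + 3), or state that windows run from the previous dose and keep 33.

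The cost is a few SAP clauses and the matching dataset flags. No new data are needed.
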